#### **2.7.1.2 Serious adverse event**

All serious adverse events (SAE) defined as per ICH guidelines and other adverse events must be recorded on case report forms. In addition, all “reportable” serious adverse events are subject to expedited reporting using the CCTG SAE form. The term ‘reportable SAE’ is used in the definitions which follow to describe those SAEs which are subject to expedited reporting to CCTG.

## Definition of a Reportable Serious Adverse Event

- All serious adverse events which are unexpected and related to protocol treatment must be reported in an expedited manner (see Section 11.2 for reporting instructions). These include events occurring during the treatment period (until 30 days after last protocol treatment administration) and at any time afterwards.
- Unexpected adverse events are those which are not consistent in either nature or severity with information provided in section 3.
- Adverse events considered related to protocol treatment are those for which a relationship to the protocol treatment cannot reasonably be ruled out.
- A serious adverse event (SAE) is any adverse event that at any dose:
  - results in death
  - is life-threatening
  - requires inpatient hospitalization or prolongation of existing hospitalization (excluding hospital admissions for study drug administration, transfusional support, scheduled elective surgery and admissions for palliative or terminal care)
  - results in persistent or significant disability or incapacity
  - is a congenital anomaly/birth defect

Medical and scientific judgement should be exercised in deciding whether expedited reporting is appropriate in other situations such as important medical events that may not be immediately life-threatening or result in death or hospitalization but may jeopardize the patient or may require intervention to prevent one of the events listed above.

Serious adverse events that are both serious and unexpected and thought to be related to protocol treatment are CCTG reportable to a Health Canada. SAEs will be listed by treatment arm. (table 32).

Of special interest, the spinal adverse events will be presented by treatment arm.

### ***2.8 Off study and death***

Patients off-study (off protocol treatment): Number and % of all treated patients.

Reason for going off-study: Number and % of all treated patients will be presented. (Table 33)

Deaths within 30 days from the last treatment.

Cause of death within 30 days from the last treatment: Number and % of all treated patients will be presented by treatment arm. (table 34)

### ***2.9 Quality of Life***

## 2.9.1 Definitions and Variables

### 2.9.1.1 EORTC QLQ-C30

There are five functional domains and three symptom domains that can be derived from EORTC QLQ-C30 (see below for definitions). If the number of unanswered questions in each domain is within a limit specified with the definition for each domain, the score is calculated as for function domains:

$$\text{Score} = 100 - (((\text{Total score for the answered questions} / (\text{no. of questions answered})) - 1) * 100 / 3)$$

And for symptom domains:

$$\text{Score} = (((\text{Total score for the answered questions} / (\text{no. of questions answered})) - 1) * 100 / 3)$$

Otherwise, the score will be recorded as “missing”. For each single item, the score will be recorded as “missing” if the answer to this item is missing.

#### Functional Domains:

X	Physical:	Questions: 1, 2, 3, 4, 5
	Score=missing if number of above questions not answered is greater than 2;	
X	Role:	Questions: 6, 7
	Score=missing if number of above questions not answered is greater than 0;	
X	Emotional:	Questions: 21, 22, 23, 24
	Score=missing if number of above questions not answered is greater than 2;	
X	Cognitive:	Questions: 20, 25
	Score=missing if number of above questions not answered is greater than 0;	
X	Social:	Questions: 26, 27
	Score=missing if number of above questions not answered is greater than 0;	

#### Symptom Domains:

X	Fatigue:	Questions: 10, 12, 18
	Score=missing if number of above questions not answered is greater than 1;	
X	Nausea and vomiting:	Questions: 14, 15
	Score=missing if number of above questions not answered is greater than 0;	
X	Pain:	Questions: 9, 19
	Score=missing if number of above questions not answered is greater than 0.	

There are also six single items in EORTC QLC-C30 pertaining to common symptoms and one global assessment that can be derived from EORTC QLQ-C30. The single items are:

#### Single Items:

X	Dyspnea:	Question 8;
X	Sleep:	Question 11;
X	Appetite:	Question 13;
X	Constipation:	Question 16;
X	Diarrhea:	Question 17;
X	Financial:	Question 28.

They are all scored using the following formula:

$$\text{Score} = (\text{Answered score to the question} - 1) * 100 / 3.$$

The **Global Assessment** includes Questions 29 and 30. If number of these two questions not answered is greater than 0, its score will be “missing”; Otherwise,

$$\text{Score} = ((\text{Total scores for the answered questions} / (\text{no. of questions answered})) - 1) * 100 / 6.$$

### 2.9.1.2 EORTC QLQ-BM22

The EORTC QLQ-BM22 addresses disease symptoms related to bone metastasis. This 22-item module is composed of four subscales, painful sites (PS) and pain characteristics (PC) on the symptom scale and functional interference (FI) and psychosocial aspects (PA) on the functional scale. All items were scaled from 1 (not at all) to 4 (very much), in which a higher score indicates greater distress in symptom scales while a higher score in functional scale indicates greater functional ability. Each scale will be converted to a score ranging from 0 to 100.

If the number of unanswered questions in each domain is within a limit specified with the definition for each domain, the score is calculated as:

Score =  $\left(\left(\frac{\text{Total score for the answered questions}}{\text{no. of questions answered}}\right) - 1\right) * 100/3$

Otherwise, the score will be recorded as “missing”.

While for FI and PA, the scores are:

Score =  $100 - \left(\left(\frac{\text{Total score for the answered questions}}{\text{no. of questions answered}}\right) - 1\right) * 100/3$

#### Functional Domains/Symptom Domains/Items:

- painful sites (PS): Questions: 31 - 35  
Score=missing if number of above questions not answered is greater than 2;
- pain characteristics (PC): Questions: 36-38  
Score=missing if number of above questions not answered is greater than 1;
- functional interference (FI): Questions: 39-46.  
Score=missing if number of above questions not answered is greater than 4;
- psychosocial aspects (PA): Questions: 47-52  
Score=missing if number of above questions not answered is greater than 3;

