2.4 Health-Related Quality of Life

The main patient-reported outcome (PRO) of interest in this study is the secondary endpoint: worst pain scores analyzed according to the a-priori defined response categories of the International Bone Metastases Consensus Working Party Criteria. These assessments and analyses are described further in sections 10 and 14. In addition to pain scores, patients allocated to both treatment arms will complete the EORTC QLQ-C30 (core) and the QLQ-BM22 (bone metastases module) quality of life instruments.

The EORTC QLQ-C30 is the core quality-of-life questionnaire of the EORTC quality of life evaluation system [Bottomlay 2007]. It has been validated [Aaronson 1993] in both English and French and is used on several CCTG studies. The EORTC QLC-C30 consists of 30 items organized into five function domains (physical, emotional, cognitive, role, and social functioning), three symptom scales (fatigue, pain and nausea), six single item scales (sleep disturbance, constipation, diarrhea, dyspnea, appetite loss, and financial issues), and a two item global health status scale. The QLQ-BM-22 module also has been validated specifically in patients with bone metastases and is designed to be used in conjunction with the EORTC QLQ-C30 core questionnaire [Chow 2009, Zeng 2012b]. The QLQ-BM22 module consists of 22 items, divided into four sub scales, namely: descriptions of painful sites, painful characteristics, functional interference, and psychosocial aspects. All items are rated from 1 (“not at all”) to 4 (“very much”) in response to item stems (e.g.; “have you had pain while sitting?”). Items on both the core questionnaire and BM-22 module are scored according to published manuals of the EORTC as routinely used by the CCTG.

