14.7 Quality of Life Analysis

The quality of life (QoL) of patients will be assessed using EORTC QLC-C30 and the Bone Metastases module (BM22) questionnaires.

The EORTC QLQ-C30 is a self-administered cancer specific questionnaire with multi-dimensional scales. It consists of both multi-item scales and single item measures, including five functioning domains, a global quality of life domain, three symptom domains and six single items. For each domain or single item measure a linear transformation will be applied to standardize the raw score to range between 0 and 100.

BM22 has 22 questions consisting of the 4 subscales (painful sites (PS) and pain characteristics (PC) on the symptom scale and functional interference (FI) and psychosocial aspects (PA) on the functional scale). The subscale will also be linear transformed to standardize the raw score to range between 0 and 100.

The quality of life data will be analyzed to look for statistically and clinically significant differences between the study treatment groups. The standard CCTG QoL Response Analysis categorizing patients as either having improved, stable, or worsened QoL will be used as follows [Osaba 2005]. A change in score of 10 points from baseline is defined a priori as clinically relevant. For functional scales and global health status, patients will be considered to have QoL improvement if reporting a score of 10 points or better than baseline at any time of QoL assessment. Conversely, patients will be considered to have worsened QoL if reporting a score minus 10 points or worse than baseline at any time of QoL assessment without above defined improvement. Patients whose scores fall between 10-point changes from baseline at every QoL assessment will be considered as stable. In contrast to functional scales, for the determination of patient's QoL response, classification of patients into improved and worsened categories will be reversed for symptom scales.

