### ***1.3 Timing of the Analyses***

The protocol mandated final analysis will be conducted after at least 228 randomized patients have met the projected follow-up period of 6 months post completion of radiotherapy.

This document is to describe the final statistical analysis plan of the final analysis according to the study protocol.

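### The SAP's formula for the BM22 psychosocial aspects score reverses no item, so more hope (item 51) or positive feeling (item 52) lowers a score defined as higher = better

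*SAP*

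**What the plan says.** SAP 2.9.1.2 splits the BM22 into two symptom scales and two functional scales, functional interference (FI) and psychosocial aspects (PA). All items are coded 1 (not at all) to 4 (very much). For the functional scales the SAP says that "a higher score in functional scale indicates greater functional ability", and for all scales that "Each scale will be converted to a score ranging from 0 to 100".

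The symptom scales take the rescaled mean directly. The SAP then introduces a subtracted form with "While for FI and PA, the scores are", which is 100 − (mean of answered items − 1) × 100/3. The item list gives "psychosocial aspects (PA): Questions: 47-52" and the missing-item rule "Score=missing if number of above questions not answered is greater than 3". No item is marked for recoding.

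Protocol 14.7 agrees on the direction: it places "functional interference (FI) and psychosocial aspects (PA) on the functional scale". Protocol 2.4 adds that "Items on both the core questionnaire and BM-22 module are scored according to published manuals of the EORTC as routinely used by the CCTG". Neither document states that any BM22 item is reversed.

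**The concern.** The questionnaire in Protocol Appendix VI shows that the six PA items do not point the same way. Item 47 asks about feeling isolated, and items 48 to 50 about worry over mobility, dependence and future health; an answer of 4 is the worst. Item 51 asks about hope that the pain will improve and item 52 about feeling positive about one's health; an answer of 4 is the best. Subtracting from 100 turns the whole scale round. That is right for items 47 to 50 and wrong for items 51 and 52.

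If the printed formula is used, baseline PA (Table 36), PA change (Table 37) and PA response categories (Table 38) mix two opposing directions. A treatment effect on PA could be weakened, exaggerated or reversed, depending on how items 51 and 52 move relative to the other four.

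**Working it through.** **Inputs.** The formula, item list, missing-item rule and direction come from SAP 2.9.1.2, the item wording from Protocol Appendix VI, and the 10-point threshold from SAP 2.9.2.5. I compare the printed formula with the same formula after replacing items 51 and 52 by 5 minus the raw answer. Six items are answered unless stated.

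**Step size.** One category on one item moves PA by 100/(3 × 6) = 5.56 points.

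**Levels.** Both scorings span 0 to 100, but the printed one puts the ends in the wrong places.

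| Answers to items 47–52 | Meaning | Printed | Recoded |
|---|---|---|---|
| 1,1,1,1,4,4 | best state | 100 − (2 − 1) × 33.3 = 66.7 | 100 |
| 4,4,4,4,1,1 | worst state | 100 − (3 − 1) × 33.3 = 33.3 | 0 |
| 1,1,1,1,1,1 | no worry, no hope | 100 | 66.7 |
| 4,4,4,4,4,4 | full worry, full hope | 0 | 33.3 |

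Printed minus recoded is −(sum of items 51 and 52 − 5) × 100/9. It is zero only when the two answers sum to 5.

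**Changes.** Let dA be the change in the sum of items 47 to 50 and dB the change in the sum of items 51 and 52.

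- Printed change = −(dA + dB) × 100/18.
- Recoded change = −(dA − dB) × 100/18.
- Difference, printed minus recoded = −(100/9) × dB = −11.1 × dB.

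| Pattern | dA | dB | Printed | Recoded |
|---|---|---|---|---|
| Two-point gain on 51–52 only | 0 | +2 | −11.1 | +11.1 |
| Two-point loss on 51–52 only | 0 | −2 | +11.1 | −11.1 |
| One-category gain on all six | −4 | +2 | +11.1 | +33.3 |
| Gain on one of 47–50 and one of 51–52 | −1 | +1 | 0 | +11.1 |
| Gain on each of 47–50, loss on both 51 and 52 | −4 | −2 | +33.3 | +11.1 |

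**Response labels.** Ten points requires a net raw change of 2, because one raw point is 5.56 and two are 11.1. At a single assessment the scorings give opposite labels when one change is at least +2 raw points and the other at most −2. This happens exactly when |dB| ≥ |dA| + 2. A one-point change on items 51–52 alone is stable under both. SAP 2.9.2.5 classifies over all assessments: one false gain of 10 is enough for improved, while a false loss counts as worsened only if no assessment shows improvement.

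**Unanswered items.** With 5, 4 or 3 items answered, the step is 100/(3 × 5) = 6.7, 100/(3 × 4) = 8.3 or 100/(3 × 3) = 11.1. If the same three items are answered both times and item 52 is among them, a single-category rise on item 52 gives −11.1 instead of +11.1.

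**Between arms.** Printed minus recoded difference in mean PA change is −11.1 × the arm difference in mean dB. For assumed arm differences of 0, 0.25, 0.5 and 1.0 raw point this is 0, −2.8, −5.6 and −11.1 points. The documents give no data from which to choose among these.

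**The case against.** The best defence is that Protocol 2.4 already sends scoring to the EORTC manuals, so the SAP formula may be shorthand and the code may recode items 51 and 52. This stands as a limit: it cannot be shown from the documents that any reported PA result would be wrong, and the manual is not available here. The recoded figures assume that 5 minus the answer is the right rule, which I infer from the item wording and the SAP's stated direction. The defence does not rescue the SAP text. The SAP gives its own formulas, item lists and missing-item rules, and handles direction explicitly elsewhere: the QLQ-C30 global assessment, where high is good, is scored without subtraction from 100. Someone programming from SAP 2.9.1.2 would not recode the items.

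A second point is that the error cancels between arms if mean change on items 51 and 52 is the same in both. With six items answered, this is correct for the difference in mean change. It does not repair baseline levels, within-arm changes or individual response labels, and in a non-blinded trial equal change in hope cannot be taken for granted.

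Third, the reach is small and the larger examples are illustrative. Both are true, and the verdict takes account of them.

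**Conclusion.** The concern holds. As printed, the PA formula contradicts the SAP's own statement of direction for two of the six items. The error is 11.1 points per raw point of change on items 51 and 52 combined, against a response threshold of 10 points. That conclusion rests only on the formula and the item wording. How often patients would be misclassified, and whether the code follows the printed formula, cannot be known from the documents.

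Only PA is affected: one of four BM22 scales and one of 19 rows in Table 38, within a secondary endpoint. SAP 2.9.2.4 names no domain for the primary quality-of-life comparison, so whether PA enters it is open. The primary endpoint, sample size, safety, radiation site progression-free survival and overall survival are untouched. It should be fixed, but it does not threaten the trial's main conclusion.

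**What to change.** First check the direction of the PA items in the EORTC manual that Protocol 2.4 relies on, and in the analysis code. Then amend SAP 2.9.1.2 to say that items 51 and 52 are replaced by 5 minus the raw answer before the PA formula and missing-item rule are applied, and cite the manual. The order matters because PA may be averaged over as few as three answered items. If the manual prescribes something else, follow and cite it, and correct the direction the SAP states for PA. Use the resulting score in Tables 36 to 38.

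The cost is one line in the SAP, one check of the manual and code, and at most one line of code. No new data are needed, since the stored item answers can be rescored at any time.

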## 2.9.2 Analysis

All patients who have completed a baseline quality of life questionnaire (EORTC QLQ-C30 and QLQ-BM22) and at least one follow-up questionnaire are included quality of life analysis.

### 2.9.2.1 Determination of Assessment Times

The following will be the scheme to determining the time frame of a QoL assessment:

- 1) Baseline: Baseline evaluation is the QoL questionnaire collected closest, but no more than 7 days prior to, the date of randomization;
- 2) At week 4 after start of Radiotherapy: If the QoL is assessed within 2 weeks before or after the week 4 after start of Radiotherapy was given.
- 3) At 3 months after start of Radiotherapy: If the QoL is assessed within 4 weeks before or after the 3 months evaluation.
- 4) At 6 months after start of Radiotherapy: If the QoL is assessed within 4 weeks before or after the 6 months evaluation.

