4.2 Randomization

Phase II:

Patients will be randomized to receive one of the following treatments below to a planned sample size of 54.

Phase III:

Patients will be randomized to receive one of the following treatments below to a planned sample size of 228.

| Arm | Treatment(s) | Dose | Duration |
|-----|--|----------------------|--|
| 1 | Standard Conventional Radiotherapy (CRT) | 20 Gy in 5 fractions | 1 fraction a day for 5 days, Monday to Friday excluding weekends (weekend treatments are permitted, if needed) |
| 2 | Stereotactic Body Radiotherapy (SBRT) | 24 Gy in 2 fractions | 1 fraction a day for 2 days, Monday to Friday excluding weekends |

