9.1 Evaluation During and After Protocol Treatment

Patients will be evaluated during radiotherapy as well as at 4 weeks, 3 and 6 months after the end of radiotherapy.

| Investigations | | After Treatment |
|--|---|---|
| History and Physical Exam including: | 
 Physical Exam ECOG PS | As per institutional standards, perform if clinically indicated |
| Radiology | 
 MRI entire spine | At 3 and 6 months |
| Pain / Analgesic Assessment | 
 Patient Diary* | At 4 weeks and at 3 and 6 months |
| Adverse Events** | Adverse events \geq grade 2 will be recorded and graded according to the NCI Common Terminology Criteria for Adverse Events (CTCAE) (Appendix V). | During radiotherapy treatment* and post radiotherapy at 4 weeks and at 3 and 6 months |
| Health-Related Quality of Life*** | 
 EORTC QLQ-C30 and QLQ-BM22 questionnaires | At 4 weeks and at 3 and 6 months |
| Economic Analysis**** | 
 EQ-5D-5L questionnaire | At 4 weeks and at 3 and 6 months |
| Other Assessments | 
 SINS score (use scoring sheet**) | At 3 and 6 months |
| Correlative Studies*** | 
 Optional, for consenting patients only: Plasma and Serum | Immediately after the second fraction of protocol therapy |
| 
* See Appendix VII. Worst Pain to be recorded only for the site included in the radiotherapy target volume. The diary MUST capture all medications that affect pain directly (e.g. opioids, non-opioid analgesics) or indirectly (e.g. steroids, co-analgesics) as well as any pre-medications given for the protocol radiotherapy treatment. Other medications may also be listed. Site staff may assist the patient with listing medication names /routes on the diary.
 
** Report only Adverse Events \geq grade 2, using the CTCAE v 4.0. See Appendix V.
 
*** The Quality of Life and Economic Analysis questionnaires will be completed by the patient electronically. See Appendix VI.
 
* Adverse events experienced by the patient during / shortly after radiotherapy treatment, including whether the patient experienced pain exacerbation (Pain Flare) at the treated site, must be evaluated.
 
** See Appendix III.
 
*** See Section 13 and the SC.24 Specimen Collection Manual that is posted on the trial webpage.
 | | |

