If you have any questions about your diary, please telephone the study nurse or CRA listed below.

| | |
|--------|----------|
| (Name) | (Number) |
|--------|----------|

Hours of Availability: _____

INFORMATION FOR THE PATIENT

Thank you for participating in this research study.

This document is a diary that you will use to record information needed for this research study. The next two pages contain instructions to help you fill in the diary. The remainder of this document is the diary itself.

You are being asked to complete this diary:

- before you are entered into the study
- on the first day you receive radiotherapy treatment, *prior* to getting the treatment
- 4 weeks after you complete your study radiation treatment
- 3 months after you complete your study radiation treatment
- 6 months after you complete your study radiation treatment

For each time you fill in the diary, you will be asked to give us two types of information for the prior 24 hours:

- your pain **in the area of your spine that was treated with study radiotherapy**,
- how much medication you have taken

If you have any questions, please ask the Clinical Research Associate (CRA) or study nurse at your clinic to help you.

Please go to the next page.

Your Pain

We will ask you about your pain in the area of your spine that was treated with study radiotherapy.

To tell us about your pain, you will be provided with a list of numbers and asked to rate your pain by choosing one number from **0 (no pain)** to **10 (pain as bad as you can imagine)** that best describes your pain in the last 24 hours.

This is what that question looks like:

| | | | | | | | | | | | |
|---|---|---|---|---|---|---|---|---|---|----|--------------------------------|
| Please rate your pain by circling the one number that best describes your pain at its WORST in your spine (area treated with study radiotherapy) in the last 24 hours: | | | | | | | | | | | |
| 0 | 1 | 2 | 3 | 4 | 5 | 6 | 7 | 8 | 9 | 10 | |
| No pain | | | | | | | | | | | Pain as bad as you can imagine |

Some correct and incorrect sample answers are shown below:

| | | | | | | | | | | | | |
|-------------------|---|---|---|---|---|---|---|---|---|---|----|---|
| Correct: | 0 | 1 | 2 | 3 | 4 | 5 | 6 | 7 | 8 | 9 | 10 | ✓ |
| Incorrect: | 0 | 1 | 2 | 3 | 4 | 5 | 6 | 7 | 8 | 9 | 10 | ✗ |
| Incorrect: | 0 | 1 | 2 | 3 | 4 | 5 | 6 | 7 | 8 | 9 | 10 | ✗ |

Please go to the next page

Your Medication

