### **2.5.2.1 Complete pain response at 3-month post treatment**

Patients will be considered to achieve a complete pain response if they meet the criteria for complete pain response outlined in 2.5.1.1.

A table of number of patients who were not evaluable for the primary endpoint of complete pain response will be provided by treatment arm. (Table 11).

A table of number of patients meeting the primary endpoint of complete pain response at 3-month after treatment start by arm will be provided. (Table 12).

The complete pain response rate is defined as number of patients achieved complete pain response / number of patients randomized for each treatment arm. Chi-square analysis will be applied to test the complete pain response rate between the two arms and the 95% confidence interval of the rate difference (SBRT arm – CRT arm) between the two arms will be calculated. The Cochran-Mantel-Hanzeal Chi-square will be used to test the difference in the complete pain response rate stratified by stratification factors at randomization except of study center. P-value from Chi-square test without adjustment for the stratification factors will also be provided for sensitivity.

Logistic regression will be used to assess the relationship between complete pain response incidence and the following factors (Table 13):

- Treatment arm
- Age (as a continuous variable and/or as a categorical variable: below and above median);
- Gender
- Primary Malignancy
- ECOG performance status
- Worst pain score at baseline
- SINS score.

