### **2.9.2.2 Calculation of Compliance Rates**

The method used to calculate the compliance rates of QoL assessment (See Tables 35) is calculated as the number of forms received out of the number of forms expected at each assessment point defined based on the following principles:

- 1) At baseline: the number of forms expected is the total number of patients who are eligible for the study and required to fill out QoL questionnaires.
- 2) At 4 weeks , 3 months and 6 months after start of Radiotherapy: the number expected at the cycle is the total number of patients who submitted the baseline QoL form and were alive.

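### The SAP counts the 4-week QoL window from the start of radiotherapy but the visit is due after its end, so a visit about 9 to 13 days late can count on SBRT and fall outside on CRT

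*SAP*

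**What the plan says.** The protocol counts follow-up from the end of treatment. Section 9.1 states: "Patients will be evaluated during radiotherapy as well as at 4 weeks, 3 and 6 months after the end of radiotherapy", and its table puts the QoL questionnaires at those visits. Appendix I labels the same columns as post-RT. The patient diary asks for completion "4 weeks after you complete your study radiation treatment".

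SAP 2.9.2.1 counts from the start. A form belongs to the 4-week time point "If the QoL is assessed within 2 weeks before or after the week 4 after start of Radiotherapy was given". The next two rules read "At 3 months after start of Radiotherapy: If the QoL is assessed within 4 weeks before or after the 3 months evaluation" and "At 6 months after start of Radiotherapy: If the QoL is assessed within 4 weeks before or after the 6 months evaluation". SAP 2.9.2.2 defines the forms expected "At 4 weeks , 3 months and 6 months after start of Radiotherapy". SAP 2.5.2.1 describes the primary-endpoint table as "complete pain response at 3-month after treatment start by arm", although its own heading refers to the period after treatment and 2.5.1.1 is headed as post-radiation.

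The arms differ in course length. Protocol 4.2 gives SBRT in 2 daily fractions on weekdays and CRT as "1 fraction a day for 5 days, Monday to Friday excluding weekends (weekend treatments are permitted, if needed").

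**The concern.** A window counted from the start, applied to a visit scheduled from the end, is off-centre by the length of the treatment course, and that length differs by arm. The same lateness relative to the protocol schedule can therefore be inside the window on one arm and outside it on the other. The SAP has no rule for a form that falls between the 4-week and 3-month windows, so such a form has no time point.

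At stake is the arm comparison of QoL change at 4 weeks (SAP 2.9.2.3, Table 37). It could lose more CRT than SBRT forms because of how days are counted, and not because of anything patients did.

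**Working it through.** **Inputs.** Day 0 is the day of the first fraction (protocol section 6.0). The SAP window is 28 ± 14 days from the start, so days 14 to 42. The protocol due day is the day of the last fraction + 28. One fraction is given per weekday: 2 for SBRT and 5 for CRT.

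**Last-fraction day.** SBRT ends on day 1 for Monday to Thursday starts and on day 3 for a Friday start. CRT ends on day 4 for a Monday start (or if the weekend is treated) and on day 6 for Tuesday to Friday starts.

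**Allowed deviation.** Lateness allowed = 42 − due day. Earliness allowed = due day − 14.

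| Course | Last fraction | Due day | Days late allowed | Days early allowed |
|---|---|---|---|---|
| SBRT, Mon–Thu start | 1 | 29 | 13 | 15 |
| SBRT, Fri start | 3 | 31 | 11 | 17 |
| CRT, Mon–Fri | 4 | 32 | 10 | 18 |
| CRT across a weekend | 6 | 34 | 8 | 20 |

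**Band where the arms differ on the late side.** For the usual SBRT course the band is 11 to 13 days late against Monday-to-Friday CRT, and 9 to 13 days late against CRT that spans a weekend. For example, a visit 12 days late is day 41 on SBRT (accepted) and day 44 or 46 on CRT (outside). For a Friday-start SBRT course the bands shrink to day 11 and to days 9 to 11. In all these courses a visit up to 8 days late is accepted, and one 14 or more days late is outside.

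**Where a late CRT form goes.** Taking 3 months as 91 days from the start (an assumption), the next window opens on day 91 − 28 = 63. Days 43 to 62 then belong to no time point.

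**Size.** Neither document gives the spread of visit dates, so this step is an assumption shown over a range. Let the visit day be normal with mean (last fraction + 28 + delay) and standard deviation SD. Starts are spread evenly over weekdays, and CRT is not given at weekends. With a continuity correction, the share outside the window is

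P = 1 − Φ((42.5 − mean)/SD) + Φ((13.5 − mean)/SD).

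For SD 7 and no delay:

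- SBRT ending day 1: 2.69% + 1.34% = 4.03%. Ending day 3: 5.02% + 0.62% = 5.64%. Average: (4 × 4.03 + 5.64)/5 = 4.4%.
- CRT ending day 4: 6.68% + 0.41% = 7.09%. Ending day 6: 11.23% + 0.17% = 11.40%. Average: (7.09 + 4 × 11.40)/5 = 10.5%.

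| SD (days) | Mean delay (days) | SBRT outside | CRT outside |
|---|---|---|---|
| 3 | 0 | 0.0% | 0.2% |
| 5 | 0 | 0.6% | 3.9% |
| 5 | 3 | 2.3% | 12.2% |
| 7 | 0 | 4.4% | 10.5% |
| 7 | 3 | 8.0% | 20.2% |
| 10 | 0 | 15.2% | 21.0% |
| 10 | 3 | 18.7% | 28.9% |

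If every CRT course ends on day 4, the CRT figure at SD 7 falls to 7.1% (no delay) or 14.3% (3-day delay).

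**After re-anchoring.** With the window at last fraction + 28 ± 14 days, every course accepts 14 days early or late. At SD 7 both arms then lose the same share: 3.8% with no delay and 5.6% with a 3-day delay.

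**The case against.** The strongest reply is that little is affected. Patients seen on or near schedule lose nothing in either arm; only a band of a few days differs. On the early side the fixed window is more generous to CRT (18 to 20 days against 15 to 17). With visits on average 3 days early and SD 7, the shares are 4.5% and 5.3%. Weekend CRT is permitted and narrows the gap. An SBRT course prolonged to the 10-day limit in protocol 8.3.5.4 would end on day 9 and be due on day 37, leaving only 5 days of lateness, which reverses the direction for that patient. All of this stands. It limits the size but does not remove the mismatch.

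A reader might infer more than the documents support:

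- *Table 35 would show falsely low CRT compliance.* SAP 2.9.2.2 counts forms received over forms expected and does not refer to the windows. The paper questionnaire's cover page records the scheduled time point, so a late form may still be counted. The artefact is possible but not established.
- *The response analysis favours SBRT.* SAP 2.9.2.5 classifies on any assessment and does not invoke the windows. Even if a form were dropped, the direction is mixed: losing an improvement would count against CRT, but losing a worsening could help it.
- *Late forms are discarded.* The SAP has no exclusion rule. That they drop out is inferred from the gap between windows.
- *The 3- and 6-month comparisons are distorted in the same way.* Those windows are set around the 3- and 6-month evaluations, which can be read as the protocol visits. If they are counted from the start, the lateness allowed at 3 months is 27 days on SBRT and 24 or 22 on CRT, a small difference in a ±4-week window. SAP 2.9.2.4 puts the QoL primary analysis at 3 months after treatment.
- *The primary endpoint is mistimed.* The reference to treatment start in SAP 2.5.2.1 conflicts with that section's own heading and with 2.5.1.1, and no visit window is attached to the pain endpoint. It is a wording slip.

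**Conclusion.** The 4-week QoL window is anchored on the wrong event relative to the protocol schedule. With courses delivered as planned, it allows 11 to 13 days of lateness on SBRT and 8 to 10 on CRT. That follows from the documents' own schedules and needs no assumption about visit timing.

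How many forms are affected does need one. The difference between arms in out-of-window share is negligible with tight scheduling (0.2 percentage points at SD 3). It is about 6 points at SD 7 with no delay (10.5 − 4.4 = 6.1) and about 12 points at SD 7 with a 3-day delay (20.2 − 8.0 = 12.2). These figures assume normal timing, even weekday starts, no weekend CRT and no interrupted courses.

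The consequence is confined to the week-4 change comparison, a non-primary time point of a secondary endpoint. The rule is worth correcting because the correction is simple, but the documents show no bias in the primary pain result or in the 3-month QoL primary analysis.

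**What to change.** In SAP 2.9.2.1, define all three follow-up windows from the last fraction of radiotherapy and keep the ±2-week and ±4-week widths. In 2.9.2.2 and 2.5.2.1, change the references to the start of treatment so that they match the protocol's end-of-radiotherapy schedule. A sentence saying how a form outside every window is handled would also help, because a gap between the 4-week and 3-month windows remains after re-anchoring.

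The cost is a change of wording and one date variable. The Radiotherapy Report is completed at the end of treatment (protocol Appendix IV), and SAP 2.6.1 already summarises treatment duration, so the last-fraction date should be available without new data collection.
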